5.5. Replacement of Participants

No participants will be replaced at any time during this study.

5.6. Independent Data Monitoring Committee

An IDMC will monitor data to ensure the safety of the participants enrolled in this study, and evaluate the efficacy of the treatment. The IDMC will consist of an independent group of clinical and statistical experts who are not involved in the management of the current study.

The IDMC will have access to unblinded aggregated interim data to make recommendations, suggest clinical study Protocol changes, or terminate the study. An unblinded, study-independent group from the CRO will support the IDMC activities. All other study personnel will have access to blinded safety and efficacy data only.

The IDMC safety review will focus on deaths, treatment discontinuations, SAEs, events ≥ Grade 3, and AESIs. The details of the analyses will be defined in the IDMC charter.

The details regarding IDMC constitution, responsibilities, authorities, and procedures and the process by which the IDMC will make recommendations and decisions are provided in the IDMC charter. The charter also defines and documents the content of the safety summaries and general procedures (including communications).

The IDMC will meet on the following schedule:

- After the first 60 randomized participants (approximately 30 in each treatment group) complete at least the first 2 study treatment cycles (8 weeks). The IDMC will review the safety data to monitor and evaluate the safety of the combination treatment and provide recommendation on whether the combination treatments are safe.
- Following the first meeting, the IDMC will meet approximately every 6 months.
- An interim analysis for nonbinding futility is planned at approximately 20% information rate (approximately 35 PFS events) in the FL population. The interim analyses for futility will be conducted by an external unblinded statistician and will be reviewed by the IDMC; the IDMC will use the guidelines provided in Section 10.5 for recommendation of either continuation or early termination of the study at the interim analysis.
- In addition, both the sponsor and the IDMC can request ad-hoc meetings for any reasons.

All AEs meeting SAE/AESI criteria will be reviewed by the sponsor's responsible safety physician on an ongoing basis and in a blinded manner to identify safety concerns. The IDMC will be informed of SUSARs according to expedited reporting rules, and about any potential safety signals.

Following each meeting, the IDMC will recommend to the sponsor whether the study should continue according to the Protocol or may suggest changes to the Protocol based on the outcome of data review. The sponsor will make the final decision for continuation or discontinuation of the study on the basis of the IDMC's recommendation.

6. STUDY TREATMENT

6.1. Study Treatments Administered

A treatment cycle is defined as 28 calendar days and includes treatment with tafasitamab/placebo, lenalidomide, and rituximab. The treatment period for each participant starts with the first administration of study treatment on Cycle 1, Day 1 (C1D1). Study drugs are tafasitamab/placebo, lenalidomide, and rituximab. Tafasitamab, lenalidomide, and rituximab are considered IMPs (see Table 7).

Tafasitamab (12 mg/kg IV) or placebo (0.9% saline solution IV)

- Administered Cycles 1 to 3 on Days 1, 8, 15, and 22, and Cycles 4 to 12 on Days 1 and 15.
- Tafasitamab will be supplied by the sponsor to an unblinded pharmacy. The placebo will be locally sourced and delivered to an unblinded pharmacy. In case of changes in body weight, tafasitamab dosing should be based on the participant's weight as assessed at the most recent treatment cycle.

Rituximab (including biosimilars; 375 mg/m² IV)

- Administered Cycle 1 on Days 1, 8, 15, and 22, and Cycles 2 to 5 on Day 1.
- Rituximab should be administered approximately 30 minutes after the tafasitamab/placebo infusion is completed but no less than 15 minutes. Sites have the option for the sponsor to provide rituximab via the IRT. Rituximab may also be obtained by the sites, where applicable. For logistical reasons, rituximab may be administered on the day after the tafasitamab infusion, or administration may be split over 2 consecutive days, according to local practice and the institution's standard of care.

Lenalidomide (including generics) (20 mg PO QD*)

- Administered Cycles 1 to 12 on Days 1 to 21 at approximately the same time every day. Lenalidomide will be provided by the sponsor to the sites.
- *For participants with moderate renal insufficiency (creatinine clearance ≥ 30 mL/min to < 60 mL/min), the starting dose of lenalidomide must be reduced to of 10 mg daily using the same schedule. The dose of lenalidomide may be increased to 15 mg QD on Days 1 to 21 of each cycle if no Grade 3/4 lenalidomide-related toxicities occur after 2 cycles.

Table 7 presents the study treatment information.

Table 7: Study Treatment Information

	Study Treatment 1	Study Treatment 2	Study Treatment 3
Study treatment name:	Tafasitamab	Lenalidomide	Rituximab
Mechanism of action:	Fc-enhanced, humanized mAb against the pan B-cell antigen CD19	Activates and increases number of T cells and NK cells, inhibits proinflammatory cytokines by monocytes, inhibits cell proliferation, and induces inhibition of tumor growth.	Direct effects: complement-mediated cytotoxicity and ADCC.
Dosage formulation:	Powder for concentrate for solution for infusion	Capsules for oral administration	Solution for infusion
Unit dose strength(s)/ dosage level(s):	200 mg in glass vials	Various strengths (refer to the Pharmacy Manual)	Rituximab (originator or biosimilar) will be prescribed and administered according to institutional guidelines.
Administration instructions:	Administered as an IV infusion at a dose of 12 mg/kg. First infusion: 70 mL/h for the first 30 minutes and increased to 125 mL/h; total infusion duration approximately 2.5 hours. Subsequent infusions: 125 mL/h over approximately 2-hours. Tafasitamab is NOT to be administered as an IV push or bolus. ^a	Dispensed at the beginning of each cycle. Participants will self-administer lenalidomide at a starting dose of 20 mg PO QD. Participants with renal impairment will have a starting dose of 10 mg PO QD.	Administered as an IV infusion at the dose of 375 mg/m ² Rituximab will be administered under the direct supervision of clinical study site personnel. Rituximab will be administered until Cycle 5. Sites should follow product insert instructions for administration adjustments due to toxicity.
Packaging and labeling:	Supplied by sponsor in single-use 20 mL glass vials. Each vial will be labeled as required per country requirement.	Lenalidomide (including generic drugs) from a commercial source. Each container will be labeled as required per country requirement.	Commercial source
Storage:	Vials must be stored at 2°C to 8°C in the original package accessible only to the unblinded clinical study site pharmacy personnel.	As per the label.	As per the label.
Status of treatment in participating countries:	Investigational	Investigational Considered non-IMP in Japan	Investigational Considered non-IMP in Canada, Australia, South Korea, Taiwan, and Turkey

^a The infusion rate escalation schedules in this Protocol and the Pharmacy Manual are recommendations. If required, the investigator should use clinical judgment to optimize participant safety by administering the infusion more slowly.

6.2. Preparation, Handling, and Accountability

6.2.1. Tafasitamab/Placebo Preparation

Reconstitution of tafasitamab vials will yield 40 mg/mL tafasitamab in 25 mM sodium citrate, 200 mM trehalose, and 0.02% (w/v) polysorbate 20 at pH 6.0. Each product vial is intended to deliver 200 mg of tafasitamab in 5 mL of reconstituted solution. The solution is colorless to slightly yellow and should be free of foreign particles; the solution may contain a few whitish product-related particles.

For administration, reconstituted tafasitamab will be diluted into a commercially available infusion container with 0.9% (w/v) sodium chloride for injection to achieve a diluted tafasitamab solution concentration between 2 and 8 mg/mL. Infusion container volumes should be 250 mL; however, participants weighing less than 42 kg or above 160 kg will require a different size infusion bag to ensure the concentration of tafasitamab is between 2 and 8 mg/mL. Refer to the Pharmacy Manual for guidance.

Tafasitamab infusion bag preparation should be prepared using an aseptic technique and administered at the clinical study site according to direction from the sponsor. Details for tafasitamab reconstitution, preparation, and infusion are included in the Pharmacy Manual.

Participants randomized to the placebo arm will receive 0.9% saline for infusion. Refer to the Pharmacy Manual for guidance.

Materials and methods for blinding the infusion bags and infusion lines are outlined in the Pharmacy Manual and in the Blinding Procedure document.

6.2.2. Handling and Accountability of Study Treatment

In the below section, the term "investigator" also represents the investigational drug storage manager for Japan as applicable.

Each investigator is responsible for ensuring that deliveries of study drugs and other clinical study materials from the sponsor are completely and correctly received, recorded, handled, and stored safely and properly in accordance with all applicable regulatory guidelines and used in accordance with this clinical study protocol.

The investigator or designee must confirm appropriate temperature conditions have been maintained during transit for all study treatments received and any discrepancies are reported and resolved before use of the study treatment.

Only participants enrolled in the study may receive study treatment, and only authorized site staff may supply or administer study treatment. All study treatment must be stored in a secure, environmentally controlled, and monitored (manual or automated) area in accordance with the labeled storage conditions with access limited to the investigator and authorized site staff.

6.2.3. Unblinded Site Staff, Handling, and Accountability

While the investigator (or designee) has ultimate responsibility for study treatment accountability, reconciliation, and record maintenance (ie, receipt, reconciliation, and final disposition records), during the conduct of the study in order to maintain the study blind, an

unblinded team consisting of an unblinded pharmacist and an unblinded nurse/medically qualified individual to oversee the infusion administration. Blinding materials (eg, Myonex infusion bag covers and infusion line covers) are provided by the sponsor. Refer to the Blinding Procedures document for additional details.

Inventory and accountability records must be maintained by the unblinded pharmacist and only accessible by unblinded study staff members. The documents must be consistently updated by the unblinded study staff and be readily available for inspection by the unblinded study monitor and open to inspection at any time by any applicable regulatory authority. The unblinded pharmacist must maintain records that document:

- Delivery of study drugs to the study site.
- Inventory of study drugs at the site.
- Participant use of the study drugs, including lot numbers and/or vial numbers, and vial counts from each supply dispensed.
- Inventory or documentation for destruction of used vials/infusion materials.
- Return of study drugs to the unblinded pharmacist by participants (lenalidomide).

The investigational product must be used only in accordance with the Protocol. The investigator will also maintain records adequately documenting that the participants were provided the specified study drug. These records should include dates, quantities, and any available batch or serial numbers or unique code numbers assigned to the investigational product and study participants.

Completed accountability records will be archived by the site. The unblinded pharmacist will be expected to collect and retain all used, unused, and partially used containers of study drugs until verified by the study monitor, unless otherwise agreed to by the sponsor based on institutional procedures. At the conclusion of the study, the unblinded pharmacist will oversee shipment of any remaining study drug back to the sponsor or its designee for destruction according to institutional procedures. If local procedures mandate on-site destruction of the investigational supply, the site should (where local procedures allow) maintain the investigational supply until the unblinded study monitor inspects the accountability records in order to evaluate compliance and accuracy of accountability by the investigative site. At sites where the study drug is destroyed before unblinded monitor inspection, the unblinded monitors will rely on documentation of destruction per the institutional procedure.

Study drug/treatment will be dispensed at the study visits summarized in the SoA (see Table 3).

Returned study drug/treatment must not be redispensed to the participants.

Further guidance and information for the final disposition of unused study treatments are provided in the Pharmacy Manual.

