6.4. Study Treatment Compliance

Compliance with study treatment administration will be calculated by the sponsor based on study drug accountability and infusion records documented by the site staff and monitored by the sponsor/designee.

Participants should receive tafasitamab/placebo under direct supervision of clinical study site unblinded personnel. Each administration volume will be checked, and the vial code and volume per administration will be recorded in each participant's eCRF as well as in the source data. Unblinded data for tafasitamab will be captured in a separate eCRF database via the IRT system and will be monitored by an unblinded CRA. Refer to the Pharmacy Manual and Suvoda IRT Site User Manual for details.

The dosing of tafasitamab or placebo will be considered appropriate if the dose administered is $\geq 80\%$ to $\leq 120\%$ of the assigned dose per single infusion. Overdose treatment is described in Section 9.10.

Lenalidomide will be dispensed on Day 1 of each new treatment cycle. Participants will return all unused or empty lenalidomide blister packs to the clinical study site throughout the treatment period as instructed by the investigator, and keep a record of lenalidomide doses taken at home, which will be reviewed by clinical study site personnel on an ongoing basis. The clinical site personnel will document the amount of study drug received from and returned to the sponsor and dispensed to participants in accordance with local regulatory requirements. Throughout the course of the study, drug accountability records must be maintained. A participant will be considered compliant with the Protocol if the lenalidomide dose administered is $\geq 80\%$ to 100% of the assigned dosage. Overdose treatment is described in Section 9.10.

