9.6. Emergency Unblinding of Treatment Assignment

In case of a medical emergency, for a participant's safety management, the procedure for emergency unblinding is provided in the IRT or Study Reference Manual. This option may be used *only* if the participant's well-being requires the investigator to be aware of the participant's treatment assignment. If a participant's treatment assignment is unblinded, the sponsor or its designee must be notified immediately by telephone.

If an investigator, the site personnel performing assessments, or a participant is unblinded, then the participant must discontinue study treatment, unless there are ethical reasons to have the participant remain on the study treatment. In these cases, the investigator must obtain specific approval from the sponsor's (or its designee's) medical monitor for the participant to continue in the study.

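### Protocol Section 6.2.3 restricts tafasitamab/placebo supply records to unblinded staff, then requires the blinded investigator to keep them too; followed literally, this could unblind the assessor of the primary endpoint

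*Protocol*

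**What the plan says.** **Blinding.** Protocol Section 6.3 keeps participants, investigators and the study team blinded until the primary analysis. Section 3 makes investigator-assessed PFS in follicular lymphoma the primary endpoint. Two of the three key secondary endpoints, overall-population PFS and PET-CR rate, are also investigator-assessed.

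**Supply.** Under Section 6.1 and Table 7, tafasitamab is supplied by the sponsor in 200 mg vials. Of the comparator, Section 6.1 says: "The placebo will be locally sourced and delivered to an unblinded pharmacy". It is 0.9% saline.

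**Records.** Section 6.2.3 sets up an unblinded pharmacist and an unblinded person to oversee infusions. It says: "Inventory and accountability records must be maintained by the unblinded pharmacist and only accessible by unblinded study staff members". Those records cover lot or vial numbers and vial counts for each participant. Later in the same section: "The investigator will also maintain records adequately documenting that the participants were provided the specified study drug". The next sentence lists what these further records should contain: dates, amounts and "any available batch or serial numbers or unique code numbers assigned to the investigational product and study participants".

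**Storage.** Section 6.2.2 puts all study treatment in a secure area with "access limited to the investigator and authorized site staff". Table 7 in Section 6.1 makes the tafasitamab vials "accessible only to the unblinded clinical study site pharmacy personnel".

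**Vial codes.** Section 6.4 says "the vial code and volume per administration will be recorded in each participant's eCRF as well as in the source data". The sentence that follows sends unblinded tafasitamab data to a separate eCRF database, monitored by an unblinded CRA.

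**If the blind is lost.** Under Section 9.6, if an investigator is unblinded, "then the participant must discontinue study treatment, unless there are ethical reasons". Continuing then needs the medical monitor's approval.

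**The concern.** The two supplies differ in kind, so traceability data carry the allocation. A tafasitamab vial or batch number against a participant means the active arm. A saline lot, or no vial number at all, means placebo. Section 6.2.3 recognises this by closing the pharmacist's records to blinded staff, and then asks the investigator for a second set with the same kind of content.

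The blind is the main protection against assessment bias for an endpoint read by the investigator. PFS by independent review is planned, but only as another secondary endpoint outside the testing hierarchy, so it is a partial check and not a substitute. If a site acted on the investigator-record sentence, the primary result would be open to the challenge that its assessor could have known the arm.

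**Working it through.** The point is textual and contests none of the plan's figures. For context, the sample size reproduces:

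- Inputs (Protocol Table 12): HR 0.65, two-sided 5%, 80% power, 1:1, 174 events, 448 participants before 15% dropout.
- Schoenfeld: 4 × (1.960 + 0.842)² / (ln 0.65)² gives 170 events.
- Freedman: (1.960 + 0.842)² × (1.65 / 0.35)² gives 175. The stated 174 lies between the two.
- Power at 174 events: Φ(√174 / 2 × |ln 0.65| − 1.960) = 81.1%.
- Dropout: 448 / 0.85 = 527.1, rounded up to 528, as stated.

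Nothing below changes these numbers.

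**Step 1: does Section 6.2.3 contradict itself?**

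| | Pharmacist's records | Investigator's records |
|---|---|---|
| Kept by | Unblinded pharmacist | Investigator, in addition |
| Access | Unblinded staff only | No restriction stated |
| Content | Lot or vial numbers and vial counts, by participant | Dates, amounts, batch, serial or code numbers tied to product and participant |
| Drugs | All study drugs | The specified study drug; no exception |

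The investigator sentences could be reconciled with the restriction if they covered only lenalidomide and rituximab, but the definitions do not allow it. The abbreviation list and Section 6.1 both define study drugs as tafasitamab/placebo, lenalidomide and rituximab, and Section 6.1 counts tafasitamab among the investigational products. The investigator-record sentence also names no designee, although the section's opening does. The contradiction is real.

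**Step 2: would the investigator's records reveal the arm?** For lenalidomide and rituximab, no: both arms receive them. For tafasitamab/placebo, yes: only one arm has sponsor vials, so one vial or batch number is enough. The schedule allows 3 cycles × 4 + 9 cycles × 2 = 30 infusions per participant, and about 275 centres are planned. These count the occasions on which such a record could arise under the literal reading. They do not estimate how often unblinding would happen.

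**Step 3: storage.** Section 6.2.2 covers all study treatment and names the investigator. Table 7 excludes everyone but unblinded pharmacy staff from the vials. Both cannot hold for tafasitamab. Seeing stock, however, does not show who received it.

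**Step 4: Section 6.4.** The text names no role as recipient of the vial code. Section 11.2 gives both the investigator and the unblinded pharmacist access to the EDC system and makes the investigator responsible for source documents. Which eCRF and which source are meant is therefore left open.

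**The case against.** The strongest reply is that the blinding design itself is sound and only the wording is loose. Section 6.2.3 says the unblinded team exists to protect the blind and gives lot and vial records to the pharmacist. The later investigator sentences are generic, ask only for what is available, and could be met with lenalidomide and rituximab records or through an unblinded designee. Table 7 is the specific rule for the vials. The Pharmacy Manual and the Blinding Procedures document, not available here, may direct sites correctly. Independent-review PFS, ORR and DoR, and a best-response concordance analysis between investigator and independent review, are also planned.

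Much of this stands, and it rules out several stronger readings:

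- **That Section 6.4 hands vial codes to the blinded investigator.** It names no such recipient. The sentence before puts infusions under unblinded personnel, and the one after routes unblinded data elsewhere. It is ambiguous, no more.
- **That storage access or the transit-temperature check reveals a participant's arm.** Neither links a vial to a person, and Section 6.2.2 lets a designee make the transit check.
- **That sites will break the blind.** A site cannot obey the investigator-record sentence for tafasitamab/placebo without disobeying the access restriction in the same section, Table 7 and Section 6.3. Actual practice is unknown.
- **That participants will lose treatment under Section 9.6.** That needs a literal reading, an investigator who is in fact unblinded, no ethical reason to continue and no monitor approval. It is a chain of conditions and not a predicted harm.

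What does not stand is the claim that the text can be left alone. The harmless reading works only by ignoring the protocol's own definition of study drug, and manuals should not have to overrule a protocol sentence.

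**Conclusion.** The text is wrong as written: Section 6.2.3 contradicts itself, Section 6.2.2 conflicts with Table 7, and Section 6.4 is unclear. A site following the investigator-record sentence literally for tafasitamab/placebo could unblind the assessor of the primary endpoint and of two key secondary endpoints. This is a stated rule that would compromise the blind if obeyed, so it should be corrected even though the unblinded team and separate database are sensibly designed.

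The size cannot be given. The documents offer no basis for estimating how many sites would act on the sentence or how far assessments would shift. Events, power and sample size do not change.

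The conclusion assumes that placebo carries no matching sponsor vial or code, as Sections 6.1 and 6.2.1 describe, and that no unseen manual formally overrides the protocol text.

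**What to change.** **Section 6.2.3.** Limit the investigator-record sentences to lenalidomide and rituximab. State that tafasitamab/placebo batch, vial and quantity records are kept only by the unblinded pharmacist.

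**Section 6.2.2.** Add that receipt of, and storage access to, tafasitamab/placebo are limited to unblinded pharmacy personnel, to match Table 7.

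**Section 6.4.** State that vial codes and vial counts go only to the separate unblinded database and to unblinded source documents.

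**Main eCRF.** Keep the arm-neutral fields the analysis uses: infusion given, whether the entire infusion was administered, prepared and administered volume, and reasons for interruption, delay or skipping. SAP Section 6.5.1 needs the completion and volume fields for dose intensity, and SAP Section 6.7 needs the reasons. Neither uses a vial code, so no planned analysis is lost. Confirm in the Pharmacy Manual that placebo bags are prepared to the same volume as active bags, so that prepared volume is in fact neutral.

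**Cost.** Amended wording in three sections, a memo to sites, and removal of the vial-code field from the blinded eCRF and source if it was built there. No new staff or systems are needed: the unblinded pharmacist, infusion overseer, monitor and database are already in the protocol.
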